7.3.9 Endocrine Parameters at Screening

At screening, the following panel of endocrine parameters will be evaluated: AMH, TSH and prolactin.

The sample will be analyzed at a central laboratory.

The results for TSH and prolactin must be available prior to randomization. The investigator will review and evaluate the laboratory results. The laboratory report will be signed and dated by the investigator.

7.3.10 Vital Signs

Systolic and diastolic blood pressure and pulse will be measured at screening, on stimulation day 1, and at end-of-cycle in the fresh cycle. In any cryopreserved cycle, vital signs will be measured at cycle initiation and at end-of-cycle. Assessments of blood pressure and heart rate are to be measured while the subject is in supine position after resting for 3 minutes.

7.3.11 Ovarian Volume

As part of the transvaginal ultrasounds performed on stimulation day 1, stimulation days 6 to 20, and end-of-stimulation, the size – length, width and depth (recorded in mm) – of each ovary is measured and used for subsequent calculation of ovarian volume.

7.3.12 Endometrial Evaluation in Cryopreserved Cycles

Transvaginal ultrasound of the uterus to measure the endometrial thickness prior to transfer will be conducted in the cryopreserved cycles. In programmed cryopreserved cycles, the transvaginal ultrasound will be performed after 10-12 days of estradiol treatment (a second assessment may be performed within 7 additional days, if applicable). In natural cryopreserved cycles, the transvaginal ultrasound will be performed on the day of confirmation of LH surge.

7.3.13 Concomitant Medication

The use of any concomitant medication within the last 3 months prior to informed consent for participation in the trial (except medication used in previous infertility treatment cycles which will be recorded as part of the infertility history) and throughout the trial will be recorded. Recording of concomitant medication will be performed at all visits. Any changes in concomitant medications or treatments must be recorded at each visit.

E-Study Protocol-22377; Ver. 1.0 Supersedes: None Page 107 of 159

Date: 25 Apr 2018

7.3.14 Drug Dispensing and Accountability

For all medicinal products used in the fresh cycle and the cryopreserved cycles, dates of administration and dose administered will be recorded. Furthermore, time of administration will also be recorded for IMP, GnRH antagonist, hCG and GnRH agonist in the fresh cycle. Details on drug dispensing and accountability are provided in section 5.6.

7.3.15 End-of-cycle Form

An end-of-cycle form must be filled in at the subject's last visit in each cycle, irrespective of whether the subject completes the cycle or not. Completion / discontinuation status will be recorded, as well as date and reason for discontinuation in case the subject did not complete the cycle.

7.4 Assessments Related to Post-trial Endpoints

7.4.1 Live Birth

Each cycle with an ongoing pregnancy will be followed until delivery. The outcome of each delivery, i.e. live birth or stillbirth, will be recorded.

7.4.2 Live Birth of Singletons Born at Term

Based on recordings of timing of blastocyst transfer as well as timing and outcome of delivery, the live birth rate of singletons born at term (≥37 weeks of gestation) will be calculated.

7.4.3 Time to Live Birth of a Singleton Born at Term

Based on the recordings of start of controlled ovarian stimulation (date) as well as timing (date) and outcome of delivery, the time to live birth of a singleton born at term will be calculated. Furthermore, based on the recording of which cycle the live birth of a singleton at term occurred in, the number of cycles before achieving this will be determined.

7.4.4 Minor/Major Congenital Anomalies

All neonates will be followed as part of the post-trial follow-up. Congenital anomalies detected at birth, 4 weeks and 1 year after birth for all infants born after the fresh cycle and after the cryopreserved cycles will be reported and classified as minor or major as described in section 8.5.1.

Date: 25 Apr 2018 E-Study Protocol-22377; Ver. 1.0 Supersedes: None Page 108 of 159

7.5 Other Post-trial Assessments

Gender, birth weight and length, and Apgar score after 1 and 5 minutes will be recorded.

Furthermore, admission to neonatal intensive care unit (NICU), neonatal care unit (NCU) or pediatric care unit (PCU) will be recorded as described in section 8.5.1. At 4 weeks and 1 year after birth, the information collected will include minor/major congenital anomalies, admission to NICU, NCU or PCU and any other relevant medical conditions.

7.6 Optional Exploratory Analyses

7.6.1 Genome Sequencing

For subjects who have provided a separate informed consent, a blood sample and a saliva sample for potential future genome sequencing will be collected on stimulation day 1. The informed consent for these optional exploratory analyses signed by the subject must be obtained prior to the sampling.

Resultant sequence data may be used in exploratory pharmacogenomic analyses aimed at identifying novel relationships between ovarian response/associated outcomes and subjects' genomic variants.

Results of these potential future exploratory analyses will not be provided to the sites.

7.6.2 Microbial Profiling

For subjects who have provided a separate informed consent, a tongue coat sample for potential future microbial profiling will be collected on stimulation day 1 and at the transfer visit(s) in the fresh and cryopreserved cycles, as applicable. The informed consent for these optional exploratory analyses signed by the subject must be obtained prior to the sampling.

Subjects will be asked to rinse and gargle twice with sterile water prior to using a tongue scraper to collect the tongue coat from the posterior middle area to the anterior middle area.

Analyses may be performed to identify relationships between ovarian response/associated outcomes and subjects' microbiome.

Results of these potential future exploratory analyses will not be provided to the sites.

Follitropin Delta, FE 999049 Solution for Injection Clinical Trial Protocol Trial Code: 000002 Date: 25 Apr 2018 E-Study Protocol-22377; Ver. 1.0

> Supersedes: None Page 109 of 159

7.7 Handling of Biological Samples

A trial-specific laboratory manual will be provided to the participating sites, describing in detail how to handle, store and transport the biological samples (blood) in this trial. Biological samples will be analyzed at central laboratories and will be maintained in storage and destruction will take place within 2 years after reporting of the trial. Exceptions are the blood, saliva and tongue coat samples collected for potential future genome sequencing and microbial profiling, as well as blood samples for which methods / results have not been adequately validated; these will be stored for a maximum of 10 years after reporting of the trial prior to destruction in line with local regulations. Blood samples analyzed by a local laboratory, e.g. in connection with eligibility criteria, estradiol for monitoring of ovarian response, and the β hCG tests, will be destroyed after analysis. For all biological samples collected in the trial, it applies that analyses beyond those described in the protocol can only be performed after obtaining the required approvals. The processes related to handling of biological samples will be described in the informed consent documents, and biobank / data protection legislation will be adhered to.

Date: 25 Apr 2018 E-Study Protocol-22377; Ver. 1.0 Supersedes: None Page 110 of 159

8 ADVERSE EVENTS

8.1 Adverse Event Definition

An adverse event is any untoward medical occurrence in a subject participating in a clinical trial. It includes:

- Any unfavorable and unintended sign, symptom or disease temporally associated with the use of the IMP, whether or not considered to be caused by the IMP.
- Adverse events commonly observed and adverse events anticipated based on the pharmacological effect of the IMP.
- Any laboratory abnormality, vital sign or finding from physical or gynecological examination assessed as clinically significant by the investigator [note: pre-existing conditions diagnosed through assessments and examinations at the screening visit or during the screening period are not adverse events, but are recorded as medical history].
- Accidental injuries, reasons for any change in medication (drug and/or dose), reasons for any
 medical, nursing or pharmacy consultation, or reasons for admission to hospital or surgical
 procedures.

All adverse events will be coded by Ferring Global Pharmacovigilance using MedDRA (the version effective at trial start).

8.2 Collection and Recording of Adverse Events

8.2.1 Collection of Adverse Events

The investigator must monitor the condition of the subject throughout the trial from the time of signed informed consent for participation in the trial until the end-of-cycle visit in the fresh cycle. In any cryopreserved cycle, adverse events will be recorded from cycle initiation until the end-of-cycle visit.

The sources of adverse events cover:

- The subject's response to questions about her health (a standard non-leading question such as "How have you been feeling since your last visit?" is asked at each visit).
- Symptoms spontaneously reported by the subject.
- Investigations and examinations where the findings are assessed by the investigator to be clinically significant changes or abnormalities.
- Other information relating to the subject's health becoming known to the investigator (e.g. hospitalization).

Trial Code: 000002 Date: 25 Apr 2018 E-Study Protocol-22377; Ver. 1.0

> Supersedes: None Page 111 of 159

8.2.2 Recording of Adverse Events

The investigator must record all adverse events in the Adverse Event Log provided in each subject's eCRF with information about:

- Adverse event
- Date and time of onset
- Intensity
- Causal relationship to IMP
- Action taken to IMP
- Other action taken
- Date and time of outcome
- Outcome
- Seriousness

Each of the items in the Adverse Event Log is described in detail in the following sections.

Adverse Event

Adverse events should be recorded as diagnoses, if available. If not, separate signs and symptoms should be recorded. One diagnosis/symptom should be entered per record.

If a subject suffers from the same adverse event more than once and the subject recovers in between the events, the adverse events should be recorded separately. If an adverse event changes in intensity, a worst-case approach should be used when recording the event, i.e. the highest intensity and the longest duration of the event.^f

Note: a procedure is not an adverse event; the reason for conducting the procedure is. Hospitalization is not an adverse event; the reason for hospitalization is. Death is not an adverse event, but the cause of death is (an exception is sudden death of unknown cause, which is an adverse event).

Ferring Pharmaceuticals

Exception: if an adverse event with onset before the first IMP administration (i.e. a pre-treatment adverse event) worsens in intensity, this must be recorded as two separate events. The initial adverse event should be recorded with outcome "not recovered" and the date and time of outcome is when the intensity changed. The second adverse event should be recorded with date and time of onset when the intensity changed.

Date: 25 Apr 2018 E-Study Protocol-22377; Ver. 1.0 Supersedes: None Page 112 of 159

Date and Time of Onset

The date of onset is the date when the first sign(s) or symptom(s) were first noted. If the adverse event is an abnormal clinically significant laboratory test or outcome of an examination, the onset date is the date the sample was taken or the examination was performed.

Intensity

The intensity of an adverse event must be classified using the following 3-point scale:

Mild: Awareness of signs or symptoms, but no disruption of usual activity.

Moderate: Event sufficient to affect usual activity (disturbing).

Severe: Inability to work or perform usual activities (unacceptable).

Causal Relationship to IMP

The possibility of whether the IMP caused the adverse event must be classified as one of the following:

Reasonable possibility:

There is evidence or argument to suggest a causal relationship between the IMP and the adverse event. The adverse event may occur as part of the pharmacological action of the IMP or may be unpredictable in its occurrence.

Examples:

- Adverse events that are uncommon but are known to be strongly associated with IMP exposure.
- Adverse events that are not commonly associated with IMP exposure, but the event occurs in association with other factors strongly suggesting causation, such as a strong temporal association or the event recurs on rechallenge with the IMP.

No reasonable possibility:

There is no reasonable evidence or argument to suggest a causal relationship between the IMP and the adverse event.

Examples:

• Known consequences of the underlying disease or condition under investigation.

Date: 25 Apr 2018 E-Study Protocol-22377; Ver. 1.0 Supersedes: None Page 113 of 159

• Adverse events common in the trial population, which are also anticipated to occur with some frequency during the course of the trial, regardless of IMP exposure.

Action Taken to IMP

The action taken to the IMP in response to an adverse event must be classified as one of the following:

- No change (medication schedule maintained or no action taken)
- Discontinued
- Interrupted
- Dose reduced
- Dose increased

Other Action Taken

Adverse events requiring therapy must be treated with recognized standards of medical care to protect the health and well-being of the subject. Appropriate resuscitation equipment and medicines must be available to ensure the best possible treatment of an emergency situation.

If medication is administered to treat the adverse event, this medication should be entered in the Concomitant Medication Log.

Date and Time of Outcome

The date and time the subject recovered or died.

Outcome

The outcome of an adverse event must be classified as one of the following:

- Recovered (fully recovered or the condition has returned to the level observed at initiation of trial treatment)
- Recovered with sequelae (resulted in persistent or significant disability/incapacity)
- Recovering (the event is improving)
- Not recovered
- Fatal

Date: 25 Apr 2018 E-Study Protocol-22377; Ver. 1.0 Supersedes: None Page 114 of 159

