8.6 Follow-up of Adverse Events and Serious Adverse Events

8.6.1 Follow-up of Adverse Events with Onset during the Trial

During the trial, the investigator must follow-up on each adverse event until it is resolved or until the medical condition of the subject is stable.

After the subject's last visit, the investigator must follow-up on any adverse event classified as serious or considered to have a reasonable possible causality to the IMP until it is resolved or until the medical condition of the subject is stable. All such relevant follow-up information must be reported to Ferring. Follow-up should continue until the outcome of recovered, recovered with sequelae or fatal, has been reached. Further, if the event is a chronic condition, the investigator and Ferring may agree that further follow-up is not required.

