10.2 Adverse Events

Adverse events will be coded using MedDRA using the version effective at trial start. Adverse events will be grouped according to start of IMP as follows:

- Pre-treatment adverse event, i.e. any adverse event occurring after signed informed consent and before start of IMP, or a pre-existing medical condition that worsens in intensity after signed informed consent but before start of IMP.
- Treatment-emergent adverse event in the fresh cycle, i.e. any adverse event occurring after start of IMP and before the end-of-cycle visit, or a pre-treatment adverse event or pre-existing medical condition that worsens in intensity after start of IMP and before the end-of-cycle visit.
- Adverse events in cryopreserved cycles, i.e. any adverse event occurring after initiation of a cryopreserved cycle and before the end-of-cycle visit, or a pre-existing medical condition that worsens in intensity after initiation of a cryopreserved cycle and before the end-of-cycle visit.

Treatment-emergent adverse events and adverse events in cryopreserved cycles will be presented in summary tables and listings. Separate summary tables will be produced for treatment-emergent adverse events in the fresh cycle and adverse events in cryopreserved cycles cumulatively (overall and by programmed and natural cycles separately). Summaries will also be provided for the trial across fresh and cryopreserved cycles.

Pre-treatment adverse events will be presented in a listing only.

Treatment-emergent adverse events will be tabulated by system organ class alphabetically and PT in decreasing order of frequency. The following will be presented: number of subjects reporting an adverse event, the percentage of subjects with an adverse event, and the number of events reported.

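### A symptom that starts in the fresh cycle and worsens in a cryopreserved cycle is tabulated at its later severity under the fresh cycle and is missing from the cryopreserved-cycle tables

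*Protocol*

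**What the plan says.** **Recording.** Protocol 8.2.2 sets the rule for a change in intensity: "If an adverse event changes in intensity, a worst-case approach should be used when recording the event". It keeps a single entry at the worst intensity reached and over the longest duration. Onset is fixed at the start: "The date of onset is the date when the first sign(s) or symptom(s) were first noted". A repeat of the same event gets its own entry only under a recovery condition: if "the subject recovers in between the events, the adverse events should be recorded separately". The footnote gives one exception, which makes two records: "if an adverse event with onset before the first IMP administration (i.e. a pre-treatment adverse event) worsens in intensity". In that case the second record takes its onset from the date the intensity changed. The log items listed in 8.2.2 include one onset, one intensity and one causality rating, and no date of worsening.

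**Follow-up.** Under Protocol 8.6.1, "the investigator must follow-up on each adverse event until it is resolved" or the subject's condition is stable. A fresh-cycle record can therefore still be open when a cryopreserved cycle begins.

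**Tabulation.** SAP 10.2 (and Protocol 9.8.2.1, in the same terms) puts in the fresh-cycle class "any adverse event occurring after start of IMP and before the end-of-cycle visit", plus pre-treatment events and pre-existing conditions that worsen in that window. The cryopreserved class takes events occurring after such a cycle starts, plus "a pre-existing medical condition that worsens in intensity after initiation of a cryopreserved cycle". The two phases are tabulated separately, with tables of adverse events and of adverse reactions by intensity for each. A summary across the whole trial is also produced.

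**The concern.** The footnote supplies the second record, with its own onset date, that the fresh-cycle class needs in order to pick up worsening of a pre-treatment event. Nothing comparable exists at the start of a cryopreserved cycle. An unresolved fresh-cycle symptom that worsens there keeps its fresh-cycle onset and takes on the later severity. The fresh-cycle table then shows an intensity that was not reached in that cycle, and the cryopreserved table shows nothing.

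The situation is plausible. Protocol 1.3 lists headache, nausea, vomiting and breast tenderness among the reactions to FE 999049, and the same four for estrogen, which is given in programmed cryopreserved cycles. The record also carries a single causality rating. An event judged related to IMP in the fresh cycle can therefore enter the fresh-cycle adverse-reaction table at a severity that arose later under other medication.

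What is at stake is the accuracy of the descriptive safety tables by phase and intensity.

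**Working it through.** The plan states no figure on this point, so there is nothing to reproduce. The check traces four event histories through the rules of Protocol 8.2.2 and the classes of SAP 10.2.

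| History | Records under 8.2.2 | Where SAP 10.2 puts it |
|---|---|---|
| Mild before first IMP dose, severe in a cryopreserved cycle | Two (footnote); second has onset at worsening | Second record: cryopreserved, severe |
| Mild in fresh cycle, recovers, recurs as severe in a cryopreserved cycle | Two (recovery in between) | Each in its own phase, at its own intensity |
| Mild in fresh cycle, never recovers, severe in a cryopreserved cycle | One; fresh-cycle onset, severe | Fresh cycle, severe; nothing in cryopreserved |
| Mild in one cryopreserved cycle, never recovers, severe in the next | One; cryopreserved onset, severe | Cryopreserved, severe (cycles pooled) |

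Only the third row goes wrong. The first and third rows differ only in when the symptom began, yet the same worsening in the same cryopreserved cycle is reported under different phases.

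Reading an ongoing fresh-cycle event as a pre-existing medical condition would not rescue the third row. There would still be no second record, and no worsening date from which to derive one.

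**Size per event.** Inputs:
- Planned arms of 500 (FE 999049) and 50 (placebo), from Protocol 9.1.
- The denominator is all subjects in the arm's safety set, from SAP 10.1.

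Shift in the fresh-cycle percentage at the higher intensity, per event:
- FE 999049: 1/500 = 0.002, i.e. 0.2 points.
- Placebo: 1/50 = 0.02, i.e. 2 points.

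These are maxima. The percentages count women, so a woman who already has another fresh-cycle event at that intensity adds nothing. With the same denominator, the cryopreserved table falls short by at most the same amount per event.

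**Number of events.** The documents do not give it. As an assumption for scale only, 1 to 5 such events on FE 999049 would shift the percentage by at most 1 x 0.2 = 0.2 to 5 x 0.2 = 1.0 points.

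**The case against.** The strongest reply is that the SAP never undertakes to move fresh-cycle adverse events into the cryopreserved class. Its worsening clause there names only pre-existing medical conditions, whereas the fresh-cycle clause also names pre-treatment adverse events. Taken literally, the plan assigns fresh-cycle events by onset. This is right as far as it goes. A reader might infer that the SAP defines a class it cannot derive, and the wording does not support that. What stands is that the literal rule reports a severity under a phase in which it did not occur.

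Further limits also stand:
- **Several cryopreserved cycles.** A reader might extend the problem to events that start in one cryopreserved cycle and worsen in another. SAP 10.2 pools these cycles cumulatively, so only the split between programmed and natural cycles could be affected.
- **Examination findings.** Protocol 7.3.7 and 7.3.8 require clinically significant changes since cryopreserved-cycle initiation to be recorded as adverse events. That may create a new record, although the text does not say how it fits the single-record rule. Events known only from symptoms have no such route.
- **OHSS.** It has its own form, its own grading and a definition of early and late onset (Protocol 7.2.7 and 8.3.1, SAP 10.8). It does not depend on the intensity field.
- **Audit trail.** Protocol 10.2 keeps dated corrections in the eCRF, so a later upgrade of intensity leaves a trace. The trace dates the entry and not the worsening.
- **Purpose of the split.** A reader might infer that the phases are separated in order to distinguish IMP effects from those of cryopreserved-cycle medication. The documents do not say so. They group events by start of IMP and rate causality event by event.

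Finally, the tables are descriptive, and the rule overstates fresh-cycle severity instead of hiding it. That is fair for the fresh cycle. For the cryopreserved cycles the same rule understates.

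**Conclusion.** The point holds in a narrow form and is minor. A stated recording rule puts one kind of event (fresh-cycle onset, no recovery, worsening after a cryopreserved cycle starts) into the wrong phase of the intensity tables and leaves it out of the right one.

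The per-event size rests on the planned arm sizes. The total cannot be computed, because the documents give neither the number of women starting a cryopreserved cycle nor the frequency of unresolved events that worsen. A shift of several percentage points might be inferred, but it would need assumed inputs that nothing in the documents supports.

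Worst intensity per subject across the whole trial, OHSS timing and grade, the primary endpoint, power and alpha are essentially or wholly unaffected.

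**What to change.** 1. Extend the footnote in Protocol 8.2.2. A fresh-cycle event that is ongoing when a cryopreserved cycle is initiated, and then worsens, is closed at that date and re-recorded with onset at the date of worsening. This is the convention already used for pre-treatment events.
2. Add fresh-cycle adverse events to the cryopreserved worsening clause in SAP 10.2. Protocol 9.8.2.1 has the same clause, so change it too or list the difference in SAP section 14.
3. For data already entered, query the worsening date only for records that span a cryopreserved-cycle initiation, before database lock. The audit trail can help to find them.
4. Link the two records with a flag. Count the pair as one event, at its worst intensity, in trial-wide totals; otherwise the split would inflate the number of events reported.

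The cost is one footnote, one phrase in the SAP, a linking flag and a few data queries. No trial procedure or treatment rule changes.
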